8.2. MASKING AND DISPENSING

On Day 0, participants will receive training by trained clinical staff on the use of TrueTear consistent with their randomized assignment (intranasal or extranasal application). The serial number of the unit will be documented in the participant's CRF and device accountability log. The lot number of the tip provided to a participant will also be recorded on the appropriate case record form and device accountability log. Participants will remain masked as to which application is the active and which is the control.

8.3. PARTICIPANT TRAINING AND DISPENSING OF DEVICE

Participants will receive training to perform nasal neurostimulation and will undergo stimulation for the first time on Day 0. On Day 0, participants will be provided with a TrueTear device and a disposable tip.

For the intranasal application, participants will be instructed to place the tips of TrueTear into both nostrils simultaneously towards the top and front of the nose (as in Figure 2). They will be told to turn on the unit by holding down the + button for approximately two seconds. There are five stimulation intensity levels and participants may adjust the level by pressing the + or – buttons to obtain a gentle tingling sensation. Participants will be told they can cease stimulation by holding down the – button for approximately two seconds on the Base Unit or by withdrawing the tips from the nostrils. Participants will be asked to apply stimulation for approximately three minutes.

Figure 2 Use of TrueTear (L) Starting position and (R) Correct treatment position by inserting the tips fully into the nasal cavity

For the control (extranasal) application, participants will be instructed to place the tips of the TrueTear on the lower part of the nose (one tip on each side as in Figure 3). They will be told to turn on the unit by holding down the + button for approximately two seconds. There are five stimulation intensity levels and participants may adjust the level by pressing the + or – buttons to obtain the best tingling sensation. Participants will be told they can cease stimulation by holding down the – button for approximately two seconds on the Base Unit or by removing contact with the nose. Participants will be asked to apply stimulation for approximately three minutes.

Figure 3 Schematic showing location of Tip Assembly application for control (extranasal) application of TrueTear

8.4. CONCURRENT THERAPIES

The use of any concurrent medication, prescription or OTC, is to be recorded on the participant's CRF along with the reason the medication was taken. Concomitant medications that are considered necessary for the participant's welfare, but will not interfere with study assessments and evaluations, will be allowed during the study at the Investigator's discretion.

Concurrent enrollment in another investigational drug or device study is not permitted.

8.5. EXAMINATION PROCEDURES

[REDACTED]

[REDACTED]

[REDACTED]

- [REDACTED]
- [REDACTED]
- [REDACTED]
- [REDACTED]
- [REDACTED]
- [REDACTED]
- [REDACTED]
- [REDACTED]
- [REDACTED]
- [REDACTED]
- [REDACTED]
- [REDACTED]
- [REDACTED]
- [REDACTED]
- [REDACTED]
- [REDACTED]
- [REDACTED]
- [REDACTED]
- [REDACTED]

[REDACTED]

[REDACTED]

- [REDACTED]
- [REDACTED]

- [REDACTED]
- [REDACTED]
- [REDACTED]
- [REDACTED]
- [REDACTED]

■ [REDACTED]

■ [REDACTED]

■ [REDACTED]

■ [REDACTED]

■ [REDACTED]

■ [REDACTED]

■ [REDACTED]

■ [REDACTED]

■ [REDACTED]

■ [REDACTED]

■ [REDACTED]

■ [REDACTED]

■ [REDACTED]

[REDACTED]

[REDACTED]

[REDACTED]

■ [REDACTED]

■ [REDACTED]

■ [REDACTED]

■ [REDACTED]

■ [REDACTED]

[REDACTED]

■ [REDACTED]

■ [REDACTED]

■ [REDACTED]

■ [REDACTED]

- [REDACTED]
- [REDACTED]
 - [REDACTED]
 - [REDACTED]
 - [REDACTED]
 - [REDACTED]
 - [REDACTED]
 - [REDACTED]
 - [REDACTED]
 - [REDACTED]
 - [REDACTED]
 - [REDACTED]
 - [REDACTED]
 - [REDACTED]
- [REDACTED]
- [REDACTED]
- [REDACTED]
- [REDACTED]

8.5.4. Early Termination/Discontinuation

If a participant is discontinued from the study prior to Day 0, then all safety evaluations that are to be performed on Day 0 should be performed on the day of discontinuation (early termination) at the discretion of the Investigator. Participants who are terminated early from the study will not be replaced.

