| Device Regimen: | 
There are two applications of TrueTear planned, one intranasal (test) and one extranasal (control). Participants will receive both applications, in random sequence, one at each of the two application days (Visit 2 and Visit 3). The two applications consist of:
 
 • Active intranasal device application for a duration of approximately 3 minutes • Active but extranasal device application (control) for a duration of approximately 3 minutes |

| | |
|---|---|
| Visit Schedule: | Visit 1: Screening (Day -14 (± 11 days)) Visit 2: First application (Day 0) Visit 3: Second application / Exit (Day 14 (± 11 days)) |
| Study Population Characteristics | |
| Number of Participants: | Approximately 35 participants with dry eye will be enrolled at one site in the UK in two groups: an initial 10 participants and a second group of 25 participants to be enrolled following an interim analysis. |
| Condition/Disease: | Dry Eye Disease (DED) |
| Evaluation Criteria | |
| [REDACTED] | [REDACTED] [REDACTED] [REDACTED] |
| [REDACTED] | [REDACTED] [REDACTED] [REDACTED] [REDACTED] [REDACTED] |
| [REDACTED] | [REDACTED] [REDACTED] [REDACTED] [REDACTED] |
| General Statistical Methods and Types of Analyses Sample Size Approximately 35 completed participants will be enrolled. This is an exploratory study and no formal sample size calculation was performed. [REDACTED] [REDACTED] [REDACTED] [REDACTED] [REDACTED] [REDACTED] [REDACTED] | |

[Redacted text block containing multiple lines of blacked-out content]

TABLE OF CONTENTS

| | |
|---|----|
| STUDY SYNOPSIS | 3 |
| TABLE OF CONTENTS..... | 6 |
| TABLE OF FIGURES..... | 8 |
| LIST OF ABBREVIATIONS..... | 8 |
| 1. Introduction..... | 9 |
| 1.1. Background..... | 9 |
| 1.2. Rationale..... | 10 |
| 2. Study Objectives..... | 10 |
| 3. Clinical Hypotheses..... | 11 |
| 4. Overall Study Design..... | 11 |
| 5. Study Population..... | 13 |
| 5.1. Inclusion Criteria..... | 13 |
| 5.2. Exclusion Criteria..... | 13 |
| 5.3. Inclusion/Exclusion Exceptions..... | 14 |
| 5.4. Discontinuation Criteria (if applicable)..... | 14 |
| 6. [REDACTED]..... | |
| [REDACTED]..... | |
| [REDACTED]..... | |
| [REDACTED]..... | |
| 7. Device Description..... | 16 |
| 7.1. Study Device..... | 16 |
| 7.2. Device Accountability..... | 17 |
| 7.3. Comparator Application Arms..... | 17 |
| 7.4. Other Study Supplies..... | 18 |
| 8. Study Methods and Procedures..... | 18 |

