Participants who terminate early during the application period will be asked to complete safety assessments (if the participants agree) prior to study exit. Participants who are terminated early from the study will not be replaced.

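### Does the early-termination rule in section 8.5.4 leave participants who stop after using the device without a safety check?

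*Combined protocol and SAP*

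**What the plan says.** Section 8.5.4 (Early Termination/Discontinuation) contains one procedure and one administrative sentence. The procedure begins "If a participant is discontinued from the study prior to Day 0, then all safety evaluations that are to be performed on Day 0" and continues "should be performed on the day of discontinuation (early termination) at the discretion of the Investigator". The other sentence says that early leavers are not replaced.

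The synopsis fixes the visit days: "Visit 2: First application (Day 0) Visit 3: Second application / Exit". Section 8.3 confirms that participants "will undergo stimulation for the first time on Day 0".

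Section 4 (Overall Study Design) has its own rule: "Participants who terminate early during the application period will be asked to complete safety assessments (if the participants agree) prior to study exit".

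Section 11.4 defines the safety population as everyone who started at least one application. Section 11.6 plans to count those who completed only the first one.

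**The concern.** The section that carries the early-termination heading directs safety evaluations to people who have not yet used the device. It says nothing about those who stop after the Day 0 application and before the exit visit. That looks like a misplaced visit reference, for three reasons.

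- Nobody covered by 8.5.4 can be in the safety population.
- Appendix 2 (section 15.2.2) refers to a slit lamp examination after application, which an unexposed person cannot have.
- Section 11.6 foresees dropout after one application, yet 8.5.4 gives no procedure for it.

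If a site worked from 8.5.4 alone, someone who left after the first application might go without a closing examination. Findings that only an examination reveals, such as a change in the cornea, the nasal lining or visual acuity, could then be missed, and the safety summary could look better than it should.

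**Working it through.** The plan gives no figure to reproduce on this point. The check is some visit-window arithmetic and a side-by-side reading.

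**Visit windows (synopsis).**
- Visit 1: Day −14 ± 11, so −14 − 11 = −25 to −14 + 11 = −3.
- Visit 2: Day 0, first application.
- Visit 3: Day 14 ± 11, so 14 − 11 = 3 to 14 + 11 = 25.
- Longest participation: 25 + 25 = 50 days, which matches the maximum in sections 8.6.1 and 8.9.

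The visible schedule is therefore consistent with itself, and Day 0 is a real visit in it.

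**Which rule covers which period.**

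| Time of leaving | Applications so far | Rule in the visible text | Condition |
|---|---|---|---|
| After Visit 1, before Day 0 (3 to 25 days) | 0 | Section 8.5.4 | Investigator's discretion |
| Day 0 after application, up to Visit 3 (3 to 25 days) | 1 | Section 4 | Participant's agreement |

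The rows do not overlap. Following one rule never breaks the other, so they complement rather than contradict each other.

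**Whether the first row serves a purpose.** Section 8.1.5 assigns the randomization number at Visit 1, so enrolled but unexposed leavers can occur. Section 9 starts adverse event capture at study entry. Section 9.6 lists events that screening can cause, including corneal abrasion from the Schirmer test and reactions to the anesthetic, and section 15.2.4 adds nasal probing with cotton swabs. A check on someone leaving after those procedures is reasonable, so the Day 0 reference need not be a slip.

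**What else applies in the second row.**
- Section 5.4: every early discontinuation and its reason goes on the End of Study form and, where relevant, the adverse event form.
- Section 8.6.1: participants exited for unanticipated device effects are followed to outcome.
- Section 8.6.2: unscheduled visits may be held for safety, with adverse events assessed as a minimum.
- Section 9.1: events are recorded whether volunteered, given in answer to an open question, or found on examination.
- Section 9.5: serious events and device effects reach the sponsor within 24 hours.
- Section 15.2.2: slit lamp examination takes place at each visit.

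**Effect on the analysis.** Membership of the safety population depends on having started an application, not on having had an exit examination. An exposed early leaver stays in the denominator in either case.

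**Size.** The documents state no dropout rate. If 5% to 15% of 35 participants left after Day 0, that would be 0.05 × 35 = 1.75 to 0.15 × 35 = 5.25 people. Those percentages are assumed, and the result counts leavers, not people left unexamined.

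**The case for a change.** The best case for a change is that section 4 does not fully do the work of 8.5.4. It names no assessments, fixes no time beyond leaving the study, and depends on the participant's agreement, whereas 8.5.4 depends on the investigator's discretion. The 8.6.1 follow-up rule covers only unanticipated effects, so an exit for an anticipated one such as epistaxis falls outside it. Unscheduled visits are optional. Some findings need an examination: the visual acuity trigger in section 15.2.1, a rise of 0.22 logMAR from screening, cannot fire without a measurement. With about 35 participants, one exposed leaver is 1/35, or about 3%, of the safety data.

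Much of this stands as a description of the drafting. Section 8.5.4 does not carry through the section 4 commitment, and the conditions differ. It does not show that safety results would be wrong. A request for assessments that depends on agreement still reaches the participants in question, and a person who is withdrawing can decline an examination in any event. The visible text does not say which assessments apply, but sections 8.5.1 to 8.5.3 and the visit table in 8.6.1 are redacted and Appendix 1 is not shown. Their absence from the public text cannot be counted as an omission from the plan.

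**Conclusion.** The concern does not call for a change. It is correct that 8.5.4 reaches only unexposed participants. It is not correct that the protocol contradicts itself or leaves exposed leavers without a safety request, because section 4 makes that request and the general adverse event rules apply throughout. A site that follows the whole protocol would ask these participants to be assessed and would record their events.

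The effect on the primary comparison is nil, since no endpoint, estimate or error rate depends on this wording. The effect on the safety summary is not shown to be other than nil, and the documents offer no dropout figure from which to size one. Harmonizing the two sections would be tidier but would bring no gain in the data.

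This rests on two assumptions: that sites read section 4 as binding alongside 8.5.4, and that nothing in the redacted or unseen parts withdraws the section 4 request.

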8.6. SCHEDULE OF VISITS

8.6.1. Scheduled Visit

Participants will remain in the study for up to 50 days and will be seen at the following intervals:

| | | |
|------------|------------|------------|
| [REDACTED] | [REDACTED] | [REDACTED] |
| [REDACTED] | [REDACTED] | [REDACTED] |
| [REDACTED] | [REDACTED] | [REDACTED] |

The schedule of exams and procedures performed at these visits can be found in Appendix 1. Descriptions of exams and procedures performed during these visits can be found in Appendix 2.

Participants who are exited from the study due to unanticipated adverse device effects will be followed until their medical outcome is determined. The Investigator must provide written reports to the study Sponsor.

8.6.2. Unscheduled Visits

These visits may be performed in order to ensure participant safety. For participants reporting for an unscheduled visit, assessments performed are at the discretion of the Investigator. At minimum, AEs should be assessed. All procedures performed at an unscheduled visit will be recorded on the Unscheduled Visit CRF pages. Any procedure indicated in the CRF that is not performed should be indicated as “Not done.”

8.7. PARTICIPANT ACCOUNTABILITY

8.7.1. Completed Participants

A completed participant is one who has not been discontinued from the study and has successfully completed Visits 1 through 3.

8.7.2. Discontinued Participants

Participants may be discontinued prior to their completion of the study due to:

- AE
- Protocol deviation
- Administrative reasons (e.g., inability to continue)
- Lost to follow-up
- Pregnancy
- Sponsor termination of study
- Other

Note: In addition, any participant may be discontinued for any sound medical reason.

Notification of a participant discontinuation and the reason for discontinuation will be made to the Sponsor and will be clearly documented on the participant’s CRF.

8.8. STUDY TERMINATION

The study may be stopped at any time by the Investigator and/or Sponsor with appropriate notification.

8.9. STUDY DURATION

An individual participant's participation will involve up to three visits over a maximum of 50 days.

8.10. MONITORING AND QUALITY ASSURANCE

8.10.1. Study Monitoring

██████████ (or designees) will monitor this study in a manner consistent with applicable health authority regulations and the procedures adopted by the SOPs of ██████████. Prior to the start of the study, member(s) of Allergan, Inc. (or designees) will review the protocol, CRFs, regulatory obligations, and other material or equipment relevant to the conduct of the study with the Principal Investigator/Sub-Investigator(s) and pertinent study staff. Monitoring visits will occur as necessary during the course of the investigation to verify:

- The rights and well-being of participants are protected
- The conduct of the investigation is in compliance with the currently approved protocol/amendment, GCP and IEC requirements
- The integrity of the data
- Study device accountability
- Adequate study documentation

During the course of the study, if the Sponsor (or designee) determines that the Investigator is non-compliant with the study plan and/or applicable regulatory requirements, the Sponsor (or designee) will take written action to correct the non-compliance and to secure compliance. In addition, the Sponsor (or designee) may terminate the Investigator's participation in the study if appropriate, or if the Investigator remains non-compliant despite the Sponsor's actions. This termination will be documented in a memo or follow up letter to the Principal Investigator.

8.10.2. Recording of Data and Retention of Documents

Participant data recorded on eCRFs during the study will be documented in an anonymous fashion. The participant will only be identified by the participant number. If, as an exception, it is necessary for safety or regulatory reasons to identify the participant, the Sponsor or its representatives, and the Investigator are bound to keep this information confidential.

The Investigator must retain essential documents for at least two years after the approval of the device and for as long as it is required in the UK in compliance with the Data protection regulations. Investigator agrees to adhere to the document retention procedures when signing the Protocol Investigator's Signature page.

9. ADVERSE EVENTS

An AE is defined as any unfavorable and unintended sign (including an abnormal laboratory finding) symptom, or disease temporally associated with the use of a product but not necessarily related to the product. An AE may also be called a complication. The capture of AEs will begin with the participant's entry into the study.

9.1. ADVERSE EVENT RECORDING

All AEs spontaneously reported by the participant and/or in response to an open question from study personnel or revealed by observation, physical examination or other diagnostic procedures will be recorded on the appropriate pages of the eCRF. Any clinically relevant deterioration in clinical finding is considered an AE and must be recorded. When possible, signs and symptoms indicating a common underlying pathology should be noted as one comprehensive event.

9.2. ADVERSE EVENT EVALUATION

The Investigator should evaluate if each AE is serious, related to the study device and anticipated using the following definitions.

A serious adverse event (SAE) is defined as any untoward medical occurrence that:

- It results in death (i.e., the AE actually causes or leads to death);
- It is life threatening (i.e., the AE places the participant at immediate risk of death);
- It requires or prolongs inpatient hospitalization. If a participant is hospitalized to undergo a medical or surgical procedure as a result of an AE, the event responsible for the procedure, not the procedure itself, should be recorded as the event. For example, if a participant is hospitalized to undergo coronary bypass surgery, the heart condition that necessitated the bypass should be recorded. Hospitalizations for diagnostic or elective surgical procedures or hospitalizations required to allow outcome measurement for the study should not be recorded as SAEs:
- It results in persistent or significant disability/incapacity (i.e., the AE results in substantial disruption of the participant's ability to conduct normal life functions);
- It results in a congenital anomaly/birth defect in a neonate/infant born to a mother exposed to the device;
- It is considered a significant medical event by the investigator based on medical judgment (e.g. may jeopardize the participant or may require medical/surgical intervention to prevent one of the outcomes listed above);
- It is considered sight-threatening by the Investigator.

9.3. RELATIONSHIP OF THE AE TO THE STUDY DEVICE

| | |
|-----------------------|--|
| Definite | A clear cut causal relationship with the study device and no other possible cause |
| Probable | A causal relationship with the study device is likely although alternate etiologies are also possible |
| Possible | A causal relationship with study device is not definite, alternate etiologies are also possible |
| Not related | The AE has no causal relationship to study device and/or there is evidence of alternative etiology such as concurrent medication or illness. |
| Not applicable | The participant has not been exposed to the study device. |

The AE will be determined to be device related, making it an adverse device effect (ADE), if it is identified to have had a definite, probable or possible causal relationship to the device.

An AE is unanticipated if the nature, severity, or frequency of the event is not consistent with either the known or foreseeable risk of AEs associated with the procedures involved in the research that are described in (a) the protocol-related documents, such as the EC-approved research protocol, user manuals and the current EC-approved informed consent document, and (b) other relevant sources of information such as product labeling and package inserts; or the expected natural progression of any underlying disease, disorder, or condition of the participant(s) experiencing the AE and the participant's predisposing risk factor profile for the AE.

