9.5. ADVERSE EVENT REPORTING

All AEs that occur during the course of the study must be reported on the Adverse Event CRF. The Investigator must determine the intensity of the event.

| | |
|-----------------|--|
| Mild | Awareness of sign or symptom, but easily tolerated |
| Moderate | Discomfort enough to cause interference with normal daily activities |
| Severe | Inability to perform normal daily activities |

All SAEs and adverse device effects (ADEs) must be reported by the Investigator to Allergan in writing within 24 hours from the point in time when the Investigator becomes aware of the event.

It is the responsibility of the Investigator to promptly notify the Ethics Committee (EC) of all SAEs and unanticipated problems, per the ECs reporting requirements.

Throughout the course of the proposed study, all efforts will be made to remain alert to possible adverse experiences or untoward findings. If adverse experiences occur, the first concern will be the safety and welfare of the participant. Appropriate medical intervention will be made.

The Sponsor will immediately conduct an evaluation of any unanticipated adverse device effect. If it is determined by the Sponsor to present an unreasonable risk to study participants, all investigations or parts of the investigation presenting that risk will be terminated as soon as possible. Termination will occur not later than five working days after the Sponsor makes this determination, and not later than 15 working days after first receiving notice of the event. The Sponsor will not resume an investigation terminated under these conditions without an additional EC approval.

Contact information for reporting Serious Adverse Events:

| Sponsor Contact Information for reporting Serious Adverse Events | |
|--|------------|
| Allergan: [Redacted] | |
| ADDITIONALLY please send a copy to: [Redacted] | |
| [Redacted] | [Redacted] |
| [Redacted] | [Redacted] |
| [Redacted] | [Redacted] |
| [Redacted] | [Redacted] |
| [Redacted] | [Redacted] |
| [Redacted] | [Redacted] |

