9.6. ANTICIPATED ADVERSE EVENTS

The following is a list of potential AEs associated with the use of the device:

- Nasal discomfort or pain
- Epistaxis
- Excessive sneezing
- Nasal irritation, paresthesia or numbness post-stimulation
- Nasal infection, abrasion or inflammation

- Skin irritation or hypersensitivity
- Headache (e.g., tension, migraine, etc.)
- Facial pain
- Excessive salivation
- Sensation of teeth vibrating
- Excessive rhinorrhea
- Temporary aggravation of nasal allergies
- Allergic reaction to contact materials

The following is a list of potential AEs associated with the testing procedures at Screening:

- Ocular discomfort
- Moderate or severe conjunctival injection
- Clinically significant decrease in visual acuity
- Clinically significant increase in corneal or conjunctival epithelial defects
- With use of proxytacaine, temporary burning, stinging and conjunctival redness of the eyes
- With use of proxytacaine, a rare hyperallergic corneal reaction characterized by epithelial keratitis, sloughing of epithelium, corneal filaments and iritis
- With the Schirmer test, corneal irritation and abrasion
- Allergic reaction to contact materials

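### The Not related category in 9.3 can be met by evidence of another cause alone, so it overlaps Probable and Possible and can take a non-serious event out of the adverse device effects and out of 24-hour reporting

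*Combined protocol and SAP*

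**What the plan says.** Section 9.2 makes the definitions binding on the person who codes: "The Investigator should evaluate if each AE is serious, related to the study device and anticipated using the following definitions". Section 9.3 then gives five categories. Four of them apply once the participant has been exposed to the device:

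- Not related is worded with two limbs: "The AE has no causal relationship to study device and/or there is evidence of alternative etiology such as concurrent medication or illness". Either limb, or both, will satisfy it.
- Possible is the weakest of the three related categories, and it leaves room for other explanations: "A causal relationship with study device is not definite, alternate etiologies are also possible".
- Probable asks for more on the device side but leaves the same room: "A causal relationship with the study device is likely although alternate etiologies are also possible".
- Definite is the only related category that shuts out every other explanation.

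Not applicable is kept for participants who were never exposed. Section 9.3 goes on to make an AE an ADE "if it is identified to have had a definite, probable or possible causal relationship to the device". Not related is outside that set.

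Section 9.5 requires all AEs to be entered on the case report form. It adds that SAEs and ADEs "must be reported by the Investigator to Allergan in writing within 24 hours" of the investigator becoming aware of them. SAEs enter that rule whatever their causality. A non-serious event enters it only by being an ADE.

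**The concern.** Evidence that something else could have caused an event is not evidence that the device did not contribute. The second limb of Not related treats it as if it were. Two investigators who hold the same view of an event could each follow the protocol and code it differently, one inside the ADE set and one outside it.

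The error can run in one direction only. The loose limb can move an event from related to unrelated, never the reverse. At stake are the count of device effects, which could come out too low, and the speed at which the sponsor hears of non-serious ones.

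Section 9.6 shows where the question could arise. It lists "Temporary aggravation of nasal allergies" among the potential events of device use. A participant with that event may well have a documented nasal allergy. If the investigator takes the allergy as evidence of another cause, the second limb permits Not related for an event that the protocol itself associates with the device.

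**Working it through.** No figure in the plan is involved, so this is a check of logic. Each definition in 9.3 is applied to each combination of two judgements: how strongly the investigator believes in a device cause, and what is known of another cause. I read Possible as meaning that a device cause cannot be ruled out.

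| Device cause | No other cause in view | Other cause possible | Evidence of other cause |
|---|---|---|---|
| None | Not related | Not related | Not related |
| Not definite | Possible | Possible | **Possible and Not related** |
| Likely | Probable | Probable | **Probable and Not related** |
| Clear cut | Definite | treated as Likely | treated as Likely |

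The last row follows from the Definite wording. Once another cause is in view, Definite is no longer available and the event is handled as the Likely row.

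Two distinct combinations meet both an ADE category and Not related. Both are in the last column, where the second limb of Not related is satisfied without the first. Section 9.3 has no tie-break.

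Next, those two combinations are traced through the ADE rule in 9.3 and the reporting rules in 9.5:

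| Event | Coded as | ADE? | To sponsor within 24 hours? | On case report form? |
|---|---|---|---|---|
| Non-serious | Probable or Possible | Yes | Yes, as ADE | Yes |
| Non-serious | Not related | No | **No** | Yes |
| Serious | Probable or Possible | Yes | Yes | Yes |
| Serious | Not related | No | Yes, as SAE | Yes |

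The choice of code changes ADE status for both kinds of event. It changes 24-hour reporting only for non-serious events, and it never changes whether the event is recorded.

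Finally, the overlap is recounted under two rewordings:

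- Not related requires that there be no causal relationship, with another cause as support only. The overlap falls from 2 combinations to 0, and every row still has a category.
- And/or is replaced by and. The overlap also falls to 0, but an event with no device relationship and no evidence of another cause then has no category. Not applicable cannot take it, because the participant was exposed.

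**The case against.** The best defence is that the table can be read sensibly. Probable and Possible speak of other causes that might exist, while Not related asks for evidence of one. An investigator who thinks a device cause likely has a row that says exactly that, and nothing forces the choice of Not related. This stands in part: the wording permits the wrong code and does not compel it, so the count could be biased downward but need not be. It does not remove the overlap. The text never says that evidence of another cause displaces a likely device cause, and such evidence does not exclude a device contribution.

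The example from 9.6 has a limit too. A nasal allergy that existed beforehand is not automatically the cause of its aggravation. The example shows what the wording allows, not what investigators will do.

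Three stronger readings are tempting, and the documents do not support them:

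- A reader might infer that serious events escape prompt reporting or that events go unrecorded. Section 9.5 rules out both. It also has the Ethics Committee notified of all SAEs and unanticipated problems.
- A reader might infer that the sponsor's evaluation of unanticipated device effects is undermined. The natural examples, nasal-allergy aggravation and headache, are both listed in 9.6, so as listed they are anticipated and would not trigger that evaluation under any code. A serious unanticipated event reaches the sponsor as an SAE, and 9.4 defines the serious unanticipated effect without using the 9.3 categories. The documents give no case in which this review would be lost.
- A reader might put a size on the effect by supposing that one or two of about 35 participants are reclassified: 1/35 = 2.9%, 2/35 = 5.7%. Nothing in the documents says that one or two is the right number, so these are not estimates.

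**Conclusion.** The point holds as a drafting defect of limited reach. Two combinations of judgements satisfy both an ADE category and Not related, with no rule to choose between them. For non-serious events the choice decides both ADE status and 24-hour reporting. For serious events it decides ADE status only. The result is possible misclassification and delay, not lost data.

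The size cannot be judged. The documents do not say how often events will have both a plausible device cause and evidence of another. The analysis text after 11.7 is redacted, so how an ADE count would be used is not visible; that redaction is not a fault in the plan.

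The conclusion rests on reading and/or literally and on 9.2 making these definitions the ones to be applied. In a single-site exploratory study with two applications of about three minutes each, this is a minor point, worth making because the repair is so cheap.

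**What to change.** Make two changes in 9.3.

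1. Define Not related by the absence of a causal relationship alone, for example: *In the investigator's judgement the study device did not cause or contribute to the event. Evidence of another cause may be recorded in support of this judgement but is not sufficient for it.*
2. Add a tie-break below the table: *An event that meets more than one category takes the most related of them.*

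When the tie-break is added, it should be clear that Possible presupposes a device cause that cannot be ruled out. Read with full literalness, a relationship that is absent is also one that is not definite, and the tie-break would then pull unrelated events upward.

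Simply changing and/or to and is not enough, because of the gap shown above.

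The cost is two or three sentences of protocol text, with no new data or procedures. Any events already coded Not related on the strength of another cause would need a second look. The downside is that the device-related count and the number of 24-hour reports may be slightly higher.
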